6	SUBJECT SELECTION	9
6.1	Study Population	9
6.2	Inclusion Criteria	9
6.3	Exclusion Criteria	9
7	CONCURRENT MEDICATIONS	9
7.1	Allowed	10
7.2	Prohibited	10
8	STUDY TREATMENTS	10
8.1	Method of Assigning Subjects to Treatment Groups	10
8.2	Blinding	10
8.3	Test and Control Formulation	10
8.4	Supply of Study Medication at the Site	10
8.5	Study Medication Accountability	11
8.6	Measures of Treatment Compliance	11
9	STUDY PROCEDURES AND GUIDELINES	11
9.1	Clinical Assessments	11
9.2	Pharmacokinetic Measurements	12
10	EVALUATIONS BY VISIT	12
10.1	Visit 1	12
10.2	Visit 2 (2 weeks after Visit #1)	12
11	ADVERSE EXPERIENCE REPORTING AND DOCUMENTATION	13
11.1	Adverse Events	13
11.2	Serious Adverse Experiences (SAE)	14
11.3	Medical Monitoring	15

- 12 DISCONTINUATION AND REPLACEMENT OF SUBJECTS15**
 - 12.1 Withdrawal of Subjects15
 - 12.3 Replacement of Subjects15
- 13 PROTOCOL VIOLATIONS15**
- 14 STATISTICAL METHODS AND CONSIDERATIONS16**
 - 14.1 Data Sets Analyzed16
 - 14.2 Demographic and Baseline Characteristics16
 - 14.3 Analysis of Primary Endpoint16
 - 14.4 Analysis of Secondary Endpoints16
 - 14.5 Interim Analysis16
 - 14.6 Sample Size and Randomization16
- 15 DATA COLLECTION, RETENTION AND MONITORING16**
 - 15.1 Data Collection Instruments16
 - 15.2 Data Management Procedures17
 - 15.3 Data Quality Control and Reporting17
 - 15.4 Archival of Data17
 - 15.5 Availability and Retention of Investigational Records17
 - 15.6 Monitoring18
 - 15.7 Subject Confidentiality18
- 16 ADMINISTRATIVE, ETHICAL, REGULATORY CONSIDERATIONS18**
 - 16.1 Protocol Amendments18
 - 16.2 Institutional Review Boards and Independent Ethics Committees18
 - 16.3 Informed Consent Form19
 - 16.4 Publications19
 - 16.5 Investigator Responsibilities20

LIST OF ABBREVIATIONS

none

PROTOCOL SYNOPSIS

TITLE	PREDICTING TREATMENT RESPONSE FOR INFLAMMATORY SKIN DISEASE
SPONSOR	self
FUNDING ORGANIZATION	none
NUMBER OF SITES	1
RATIONALE	To develop a predictive algorithm to determine whether a given patient with psoriasis will respond to one of the multiple specific pathway blocking FDA-approved psoriasis biologic medications.
STUDY DESIGN	interventional trial with molecular profiling of skin samples
PRIMARY OBJECTIVE	To obtain pre-treatment psoriatic skin samples for molecular profiling prior to treatment with tildrakizumab to correlate with and to predict treatment response
SECONDARY OBJECTIVES	
NUMBER OF SUBJECTS	10
SUBJECT SELECTION CRITERIA	
Inclusion Criteria: > 18 years of age, Patients with moderate-severe psoriasis or atypical psoriasis with either non-biologic treatment failure or > 5% body surface area affected.
 
Exclusion Criteria: tuberculosis, active serious infection, active systemic malignancy, or received a systemic medication for psoriasis within 3 months of study screening.

TEST PRODUCT, DOSE, AND ROUTE OF ADMINISTRATION	Tildrakizumab 100 mg subcutaneous injection
CONTROL PRODUCT, DOSE AND ROUTE OF ADMINISTRATION	n/a

DURATION OF SUBJECT PARTICIPATION AND DURATION OF STUDY	
The time commitment for the first visit will be approximately 1.5 hours to discuss the study, consent the patient, and perform the biopsy.
 
The second visit will last approximately 15 minutes
 
The third and fourth visits will last approximately 30 minutes.
 
With a total time committment of ~ 2 hrs 45 minutes

CONCOMMITANT MEDICATIONS	
Allowed:
 
Prohibited: other systemic medications for psoriasis

EFFICACY EVALUATIONS	
PRIMARY ENDPOINT	
 molecular gene expression profiling of skin cell populations.
SECONDARY ENDPOINTS	
 Psoriasis Area and Severity Index (PASI) score
OTHER EVALUATIONS	
SAFETY EVALUATIONS	
Re-evaluation of biopsy site at follow-up visit in 14 days for wound infection
 
In person medical visit for physical exam and history 4 weeks and 16 weeks after start of medication

PLANNED INTERIM ANALYSES	
When approximately 50% of patients have completed the study through Visit 4, an interim analysis for safety will be conducted by the investigator. Serious adverse events will be monitored by the committee on an ongoing basis throughout the study.

STATISTICS Primary Analysis Plan	
We will rely heavily on RNA-seq analysis, in some cases complemented with DNA sequencing and protein assessments. The RNAseq data will be normalized and compared in diseased vs normal skin and differential expression discerned at a significance level of 5% in a single test, in a two-group comparison, using a Negative Binomial mode. Numerous qualitative analyses will be performed as well.

Rationale for Number of Subjects	
Bulk RNA-seq studies have required ~100 patients to distinguish markers for different inflammatory skin diseases. We anticipate with single cell RNA-seq, fewer patients may be necessary. This is also a pilot trial and due to the cost of the molecular profiling will start with an initially smaller # of patients.

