2 STUDY RATIONALE

The researchers want to find a way to predict whether a person with psoriasis will respond to a given medication. In this study, patient will start tildrakizumab (a FDA-approved medication for psoriasis). Prior to treatment, a small piece of psoriasis-affected skin will be sampled and molecularly profiled. We will then analyze the molecular profiles and compare to patient tildrakizumab treatment response to predict which future patients will best respond to this medication.

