3 STUDY OBJECTIVES

3.1 Primary Objective

Our primary objective is to identify the genes that are differentially expressed in psoriatic skin between patients that do and do not respond to tildrakizumab

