5 CRITERIA FOR EVALUATION

5.1 Primary Efficacy Endpoint

We will evaluate if there are genes which are statistically significantly upregulated or downregulated in specific cell populations, based on RNA sequencing.

For assessment of psoriasis improvement, we will use the Psoriasis Area and Severity Index (PASI) scoring system.

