13 STATISTICAL METHODS AND CONSIDERATIONS

Prior to the analysis of the final study data, a detailed Statistical Analysis Plan (SAP) will be written describing all analyses that will be performed. The SAP will contain any modifications to the analysis plan described below.

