13.3 Analysis of Primary Endpoint

After RNA sequencing performs, standard distribution-based statistical test for significantly overexpressed or under-expressed genes will be applied.

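### The primary test compares diseased with normal skin, so it cannot answer the primary objective of finding genes that differ between responders and non-responders

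*Combined protocol and SAP*

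**What the plan says.** **The objective concerns response.** Section 3.1 sets out to "identify the genes that are differentially expressed in psoriatic skin between patients that do and do not respond to tildrakizumab". The synopsis objective is to profile pre-treatment skin "to correlate with and to predict treatment response". Section 2 adds: "We will then analyze the molecular profiles and compare to patient tildrakizumab treatment response".

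**The named test concerns tissue type.** The synopsis Primary Analysis Plan states: "The RNAseq data will be normalized and compared in diseased vs normal skin and differential expression discerned", and continues "at a significance level of 5% in a single test, in a two-group comparison", with a negative binomial model. It also mentions qualitative analyses, without describing them. This is the only contrast in the document that has groups, a significance level and a model.

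**The remaining sections name no groups.** Section 5.1 looks for "genes which are statistically significantly upregulated or downregulated in specific cell populations". Section 13.3 says that a "standard distribution-based statistical test for significantly overexpressed or under-expressed genes will be applied". Section 5.1 names PASI as the measure of improvement, but gives no responder threshold, change measure or time point. PASI appears in none of the visit lists (Sections 9.1–9.4) and not in Appendix 1.

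**Detail is deferred.** Section 13 promises a SAP before the final data are analysed and says "The SAP will contain any modifications to the analysis plan described below".

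**The concern.** A contrast of diseased with normal skin uses only the type of tissue sampled before treatment. Its result for any gene is the same whichever patients later respond. It yields a list of genes that separate plaque from normal skin. A gene on that list may have nothing to do with response, and a gene related to response may be absent from it.

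There is also a question of timing. The study is unblinded (Section 7.2). If the response contrast is first written in a later SAP, the groups, the definition of response and the assessment time could be chosen after outcomes or expression data have been seen.

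**Working it through.** **Step 1. Objective and test side by side**

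| Element | Section 3.1 | Synopsis Primary Analysis Plan | Section 13.3 |
|---|---|---|---|
| Groups | responders, non-responders | diseased skin, normal skin | not named |
| Tissue | psoriatic skin | psoriatic and normal skin | not named |
| Uses response | yes | no | not stated |
| Model and level | none | negative binomial, 5%, single test | unspecified distribution-based test |

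No section joins the groups in the second column to a test.

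**Step 2. The plan's own figure**

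Section 13.6 says that 10 samples will detect two-fold differences. It gives no groups, power, dispersion or read depth, so the figure cannot be reproduced. It can be turned round: on the natural-log scale, the largest SD that gives 80% power (assumed) at two-sided 5% is

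SD_max = ln 2 / [(1.960 + 0.842) × √(1/a + 1/b)]

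- 10 v 10: 0.693 / (2.802 × 0.447) = 0.553
- 5 v 5: 0.693 / (2.802 × 0.632) = 0.391
- 3 v 7: 0.693 / (2.802 × 0.690) = 0.359
- 2 v 8: 0.313
- 1 v 9: 0.235

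The statement is easier to meet for 10 lesional against 10 normal samples than for 10 patients split by response. Which comparison is meant therefore changes what the sample size can support.

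**Step 3. What each test detects (simulation)**

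Assumptions, none of them in the documents: 10 lesional and 10 normal samples, treated as independent; equal library sizes; normal-skin mean count 100; dispersion 0.1, 0.2 or 0.4, treated as known; negative binomial likelihood-ratio test at 5% for one gene; 40,000 replicates per setting.

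*Gene A* is two-fold higher in non-responders, and its average over the lesional samples equals normal skin. With 3 non-responders of 10, solving 0.3 × 2x + 0.7 × x = 100 gives x = 76.9 for responders and 153.8 for non-responders.

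*Gene B* is two-fold higher in lesional skin and unrelated to response.

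| Share of trials flagged (3 non-responders) | Dispersion 0.1 | 0.2 | 0.4 |
|---|---|---|---|
| Gene A, diseased v normal | 5.5% | 5.8% | 5.8% |
| Gene A, responder v non-responder | 86% | 60% | 36% |
| Gene B, diseased v normal | 99.7% | 92% | 67% |
| Gene B, responder v non-responder | 5.0% | 5.0% | 5.2% |

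For gene A, the response test flags 77%, 50% and 30% with 2 non-responders, and 90%, 65% and 39% with 4.

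**Step 4. Multiplicity**

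A 5% level per test with no true differences gives 0.05 × 10,000 = 500 expected false positives per cell population at an assumed 10,000 genes (250 at 5,000; 1,000 at 20,000). The single-test wording would need replacing whichever contrast is primary.

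**The case against.** **The comparison is named, and a SAP is promised.** Section 3.1 gives the groups and the tissue, Section 5.1 gives PASI, and the test in Section 13.3 could be applied to that grouping. The conflict sits in one synopsis sentence; Section 13 is silent on the contrast and does not contradict the objective. Section 13 also commits to a SAP covering all analyses before the final data are analysed. This is right as far as it goes: what is missing is the analysis, not the intent. But the only contrast on file with a test is still the wrong one for the objective, and in an unblinded study the SAP could be written after PASI outcomes are known.

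**Gene A is constructed.** Its lesional average is set equal to normal skin, so a result near 5% follows by design. Other response-related genes are flagged more often by the named test. With 3 non-responders, if non-responders are at twice normal and responders at normal, the rates are 43%, 25% and 16% at dispersion 0.1, 0.2 and 0.4; in the reverse case they are 95%, 74% and 45%. This stands, and gene A should be read as an illustration. In those cases, however, the test responds to the lesional average and cannot tell such genes from gene B.

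**The 10-plus-10 layout is not in the plan.** This also stands. Section 13.6 speaks of 10 samples, Section 4.1 makes normal tissue optional, and Section 9.1 allows up to two biopsies without requiring one from normal skin. It also means that the named contrast may lack data.

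**The response comparison will be weak in a 10-patient pilot.** True. At a Bonferroni level over an assumed 10,000 genes, power for gene A with 3 non-responders is 8.6%, 1.3% and 0.1%; false-discovery-rate control could be less strict. At an assumed 80% response rate, the chance of at most one non-responder among 10 is 0.8¹⁰ + 10 × 0.2 × 0.8⁹ = 38%. Pilot status excuses low power. It does not excuse leaving the objective's variable out of the primary test.

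**Conclusion.** The concern holds, and the text must be corrected. The primary test as written does not address the primary objective, although the pre-treatment samples could. This conclusion comes from reading the sections together and needs no numerical assumption.

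The size of the loss does need assumptions. For a gene with a two-fold response difference centred on normal skin, detection falls from 30–90% (2 to 4 non-responders, dispersion 0.1 to 0.4) to about the 5% false-positive rate. A gene that marks only lesional skin is flagged in 67–99.7% of trials. These are single-gene, single-test figures; power across all genes would be lower.

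**What to change.** Amend the synopsis Primary Analysis Plan and Section 13.3 as follows.

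1. **Primary analysis.** Relate pre-treatment lesional expression to PASI-based response, with counts aggregated per patient and a negative binomial model per gene and cell population. Choose one of:
   - (a) responder versus non-responder, as in Section 3.1, with response and its time point defined in advance; or
   - (b) percent change in PASI as a continuous variable, with Section 3.1 reworded to match. This avoids depending on a very small non-responder group.
2. **Error control.** State false-discovery-rate control across genes and cell populations in place of the single-test 5% level.
3. **Diseased versus normal.** Keep it as a secondary descriptive comparison, blocked by patient where both samples exist. Reconcile this with Sections 5.2 and 13.4, which say there are no secondary endpoints, and with the synopsis, which lists PASI as one.
4. **Data needed.** Add PASI scoring before the first dose and at Visit 4 to Sections 9.1–9.4 and Appendix 1, and state that every patient gives a lesional sample.

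The amendment should be in place before PASI outcomes or expression data are examined. The cost is small: amendment and SAP text, PASI scoring at existing visits, and a clarified sampling rule. No new visits or patients are needed to align the test with the objective, but the amended plan should say plainly that 10 patients give limited power across all genes.

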4 STUDY DESIGN

4.1 Study Overview

This is a single center study in which patients with psoriasis or atypical psoriasis will donate small samples of that skin and/or normal tissue prior to treatment with the FDA-approved psoriasis medication, tildrakizumab.

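### The plan's only significance level is 5% per single test, stated for diseased versus normal skin, and nothing in it controls for testing many genes in several cell populations

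*Combined protocol and SAP*

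**What the plan says.** - **Synopsis, Primary Analysis Plan.** Expression will be "compared in diseased vs normal skin and differential expression discerned at a significance level of 5% in a single test, in a two-group comparison", with a negative binomial model. The only other 5% in the synopsis is a body surface area criterion.
- **3.1 Primary Objective.** The aim is to "identify the genes that are differentially expressed in psoriatic skin between patients that do and do not respond to tildrakizumab". This is a different contrast from diseased versus normal skin.
- **5.1 Primary Efficacy Endpoint.** The study looks for "genes which are statistically significantly upregulated or downregulated in specific cell populations, based on RNA sequencing".
- **13.3 Analysis of Primary Endpoint.** A "standard distribution-based statistical test for significantly overexpressed or under-expressed genes will be applied". No level, adjustment or unit of analysis is given.
- **13.6 Sample Size and Randomization.** Ten samples are said to be enough to detect two-fold differences. No power, variability, group split or significance level accompanies the statement.
- **Section 13, opening.** Before the final analysis, "a detailed Statistical Analysis Plan (SAP) will be written describing all analyses that will be performed".
- **Synopsis, Rationale for Number of Subjects.** "We anticipate with single cell RNA-seq, fewer patients may be necessary. This is also a pilot trial".
- **4.1 Study Overview.** Patients "will donate small samples of that skin and/or normal tissue prior to treatment", so some may give only one kind of sample.

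The available text nowhere mentions a false discovery rate, a familywise error rate or adjusted p-values.

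**The concern.** A 5% level for one test is not a rule for a search across the transcriptome in several cell populations. Applied gene by gene, it would produce a long list even if no gene differed, and the primary endpoint could then scarcely fail. Section 2 intends to "compare to patient tildrakizumab treatment response to predict which future patients will best respond to this medication", so false entries could be carried forward as candidate predictors.

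Two related gaps make this worse. The 5% level is attached to diseased versus normal skin, which leaves the contrast in 3.1 without a stated threshold. Single-cell data are also anticipated, and nothing says whether the patient or the cell is the unit of the test.

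**Working it through.** **Inputs from the documents:** 5% per single test (synopsis); 10 patients (synopsis) and 10 samples (13.6); two-fold difference, ln 2 = 0.693 (13.6).

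**Assumptions, because the documents give no values:** 10,000 to 20,000 unchanged genes per population; biological coefficient of variation (BCV) 0.4; mean count 50; splits of 5/5 and 7/3 for responders versus non-responders.

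**1. The plan's own figure.** The two-fold statement can be neither reproduced nor refuted. By normal approximation, 80% power at two-sided 5% in one test requires a log-scale SD of at most 0.693 / [(1.960 + 0.842) × √(1/n₁ + 1/n₂)]:
- 5/5: 0.693 / (2.802 × 0.632) = 0.391
- 7/3: 0.693 / (2.802 × 0.690) = 0.359
- 10 versus 10, unpaired: 0.693 / (2.802 × 0.447) = 0.553

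At 5/5, power runs from 95.5% (SD 0.3) to 34.7% (SD 0.7). The claim holds or fails on an input that is not stated.

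**2. False declarations at an unadjusted 5%.** Expected number = 0.05 × unchanged genes: 0.05 × 10,000 = 500 and 0.05 × 20,000 = 1,000 in each population.

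**3. Chance of at least one.** For independent null tests this is 1 − 0.95^k: 0.401 for k = 10, 0.642 for k = 20 and 0.994 for k = 100.

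**4. False share of the list.** With a proportion p of genes truly different, false share = 0.05(1 − p) / [0.05(1 − p) + power × p]. For example, p = 5% and power 80% give 0.0475 / (0.0475 + 0.040) = 54%.

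| Truly different | 80% power | 30% power |
|---|---|---|
| 1% | 86% | 94% |
| 5% | 54% | 76% |
| 20% | 20% | 40% |

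**5. Unit of the test.** With an assumed 100 cells per patient and within-patient correlation of 0.01 to 0.05, the design effect is 1 + 99 × 0.01 = 1.99 to 1 + 99 × 0.05 = 5.95. In the responder comparison, a nominal 5% test that treats cells as independent then rejects 16% to 42% of true nulls (normal approximation).

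**6. What control would cost in power.** This was simulated with negative binomial counts: 20,000 genes, 5% truly different, two-fold change, one population, patient as unit, moderated-variance test on log counts. The test rejected about 4.9% of true nulls. Power is shown for unadjusted 5%, then for Benjamini-Hochberg (BH) at 5%.

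| Comparison | Equal dispersion | Dispersion varying between genes (log-SD 0.5) |
|---|---|---|
| 5/5 responders | 69% to 8% | under 1% after BH |
| 7/3 responders | 62% to 3% | under 1% after BH |
| 10 vs 10 diseased/normal, unpaired | about 93% to 60% | 89% to 49% |

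The responder rows assume that the 5% level carries over to the contrast in 3.1, which the plan does not state. A repeat run agreed to within about two percentage points.

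**Sensitivity case only.** A negative binomial likelihood-ratio test with dispersion estimated gene by gene by maximum likelihood rejected about 9% of true nulls at 5/5 and 7/3. The documents do not select that method.

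**The case against.** The strongest reply is that the single-test phrase reads like sample-size language. It may describe the calculation behind 13.6 and not the analysis rule. That is possible. A reader might infer that the plan commits to unadjusted gene-by-gene testing, and the documents do not support so strong a reading. But the phrase stands under Primary Analysis Plan, and if it belongs to 13.6 the plan has no analysis threshold at all. The gap remains on either reading.

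Second, a detailed SAP is promised and may modify the plan. This stands as mitigation. The text does not commit that SAP to multiplicity control, and section 13 contains no rule for it to carry forward.

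Third, this is a 10-patient pilot with qualitative analyses alongside, and strict error control leaves little power for the responder contrast. This also stands. It argues against requiring familywise control and for a modest rating. It does not justify silence, because 3.1 and 5.1 make gene-level findings the primary aim and the plan does not label the list exploratory.

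Finally, pooling the false discovery rate across genes and populations is only one option. Control within each population is also defensible, provided the family is named beforehand.

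**Conclusion.** The concern holds as an omission: no rule governs significance across genes and cell populations, and the primary contrast in 3.1 has no threshold. If 5% is applied gene by gene, expect about 500 to 1,000 false declarations per population. That figure rests on the assumed 10,000 to 20,000 unchanged genes and a calibrated test.

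Three stronger inferences are not supported:
- **That most of the list would be false.** The share runs from 20% to 94% across the cases shown. The documents give neither the true proportion of changed genes nor the power.
- **That the two-fold statement in 13.6 is wrong.** It cannot be checked without the missing inputs.
- **That patients in the trial are affected.** All are treated, and no treatment decision in the trial rests on the gene list.

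This should be fixed before the data are analysed. Confidence is high that no rule is stated; that unadjusted testing would actually be used is only conditional.

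**What to change.** 1. In the synopsis, replace the 5% single-test wording with a prespecified false discovery rate rule, for example Benjamini-Hochberg at 5%. State whether the family is within or across cell populations.
2. Add the same rule to 5.1 and 13.3, which at present contain no threshold, and carry it into the SAP.
3. Apply it to responders versus non-responders (3.1) and, separately, to diseased versus normal skin.
4. Name the patient as the unit of the test. Specify a negative binomial or moderated test that is calibrated for small samples.
5. Report genes with unadjusted p < 0.05 only as an exploratory ranking.
6. Restate 13.6 at the threshold used, with power, dispersion and group split.

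The cost is wording and a revised 13.6, with no new data. The real downside is a much shorter, possibly empty, list for the responder contrast: under the assumptions above, power for a two-fold change is 3% to 8%, and under 1% if dispersion varies between genes. Diseased versus normal skin keeps more, about 49% to 60% for 10 versus 10 unpaired samples. The plan should say this openly.

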9 EVALUATIONS BY VISIT

9.1 Visit 1

1. Review the study with the subject (subject's legal representative) and obtain written informed consent and HIPAA authorization and assent, if appropriate.
2. Assign the subject a unique screening number.
3. Record demographics data.
4. Record medical history, including a history of rash, diagnosis date, and prior treatments.

5. Record concomitant medications.
6. Perform a complete skin examination.
7. Clean skin, anesthetize skin, take skin sample(s) (up to 2 6 mm punch biopsies), place suture.
8. Photograph of biopsied lesional skin and other psoriatic lesions
9. Part of the biopsied specimen will be sent for standard histopathology (if no previous histopathology from a similar representative lesion has been done)
10. Schedule subject for suture removal in 14 days.
11. Baseline routine bloodwork (CBC, quant gold, HIV, HB surface Ag, Anti-HB surface AB, anti-HB core AB, hepatitis C antibody, BUN/Creatinine, AST/ALT)

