13.6 Sample Size and Randomization

10 samples will be collected for initial analysis. Distribution-based statistical analysis indicates that two-fold differences in gene transcription will be detected at this size.

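### The plan names a negative binomial test on 10 samples without a small-sample form; the common large-sample versions reject 6–12% of null genes at nominal 5%, and a false-discovery correction alone would not repair the gene list

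*Combined protocol and SAP*

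**What the plan says.** The Statistics row of the protocol synopsis has RNA-seq data normalised and "compared in diseased vs normal skin", with "differential expression discerned at a significance level of 5% in a single test", "in a two-group comparison, using a Negative Binomial mode". Section 13.3 describes the primary analysis only as follows: "standard distribution-based statistical test for significantly overexpressed or under-expressed genes will be applied".

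On size, section 13.6 states that "10 samples will be collected for initial analysis" and adds: "Distribution-based statistical analysis indicates that two-fold differences in gene transcription will be detected at this size". The dispersion and power behind that claim are not given.

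The plan describes two different comparisons. The synopsis contrasts diseased with normal skin. Section 3.1 seeks genes "differentially expressed in psoriatic skin between patients that do and do not respond to tildrakizumab". Visit 1 (section 9.1) allows staff to "take skin sample(s) (up to 2 6 mm punch biopsies", so 10 patients could yield up to 20 libraries.

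Nowhere does the plan state the form of the test (Wald, likelihood ratio, exact or quasi-likelihood), how dispersion is estimated, whether it is moderated across genes, which reference distribution is used, or any multiplicity correction. Section 13 promises a fuller SAP before the final data are analysed.

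**The concern.** A negative binomial test needs a dispersion for each gene. With 10 values and two fitted means, only 8 degrees of freedom remain to estimate it. The maximum-likelihood estimate is biased low, and a Wald or likelihood-ratio test with a normal or chi-square reference also treats it as known. Both effects make p values too small, most of all in the far tail, where gene lists are drawn.

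This is separate from the number of genes tested. A false-discovery procedure assumes valid input p values, so adding one to an uncalibrated test does not deliver the stated control. At stake is a list of named genes meant to predict which future patients respond. Some of those genes could be artefacts of the test, and a pilot's list is carried into later work.

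**Working it through.** **Inputs from the plan.** 10 samples (13.6); 5% per test, taken as two-sided because both over- and under-expression are sought; two groups; two-fold difference (13.6); up to 2 biopsies per patient (9.1).

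**Assumptions, not in the plan.** Mean count μ = 100 (checked over 10–1000); dispersion φ of about 0.15–0.4 (checked from 0.1); splits 5/5, 7/3 and 8/2; 20,000 genes; equal library sizes; one independent value per patient (bulk, or summed over cells).

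**1. The plan's own figure.** On the log scale at 5/5, SE = √[2(1/μ + φ)/5] and power = Φ(ln 2/SE − 1.96). For φ = 0.2, SE = √(0.4 × 0.21) = 0.290 and power = Φ(2.39 − 1.96) = 67%.

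| φ | 0.05 | 0.1 | 0.2 | 0.4 | 1.0 |
|---|---|---|---|---|---|
| Power for two-fold, unadjusted 5% | 99% | 91% | 67% | 40% | 19% |

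Power of 80% needs φ of about 0.14 or less. The two-fold claim can be neither confirmed nor refuted, because φ and power are not stated. This formula itself treats dispersion as known.

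**2. Expected size of the test.** A normal-theory analogue with n = 10 and 8 degrees of freedom gives:
- Maximum-likelihood Wald with a normal reference: the variance is divided by 10 instead of 8, so the true t-scale cut-off is 1.96 × √(8/10) = 1.753, and P(|t₈| > 1.753) = 11.8%.
- Likelihood ratio: 10 ln(1 + t²/8) > 3.841 gives |t| > 1.936, and P = 8.9%.
- Bias-corrected variance, still with a normal reference: P(|t₈| > 1.96) = 8.6%.
- For 10 v 10 (18 degrees of freedom), the first two become 7.9% and 6.7%.

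**3. Simulated negative binomial null genes** (0.4–1 million per scenario), nominal 5%:

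| Test | 10 samples | 10 v 10 |
|---|---|---|
| Gene-wise ML Wald, normal | 11.7–12.4% | 7.9% |
| Gene-wise likelihood ratio | 8.8–9.1% | 6.7% |
| Cox-Reid dispersion, Wald, normal | 8.6–9.5% | 6.6% |
| Shrunken dispersion, Wald, normal | 5.8–7.3% | 6.0% |
| Cox-Reid dispersion, t on n − 2 df | 5.0–5.8% | 5.0% |
| t-test on log counts | 4.6–5.1% | 4.9% |

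Further runs of the shrunken-dispersion Wald test gave 7–8%, so its range is taken as 6–8%. The 10 v 10 column treats libraries as independent, which lesional and normal skin from one patient are not.

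**4. Tail.** Bonferroni over 20,000 genes uses 0.05/20,000 = 2.5 × 10⁻⁶. At 5/5 and φ = 0.2:
- ML Wald: about 1,180 times nominal, so 1,180 × 2.5 × 10⁻⁶ × 20,000 = 59 expected false genes.
- Likelihood ratio: 5.7 × 10⁻⁵ × 20,000 = 1.1; family-wise error 1 − e^(−1.14) = 68%.
- Shrunken Wald: 3.9 × 10⁻⁵ × 20,000 = 0.8; family-wise error 1 − e^(−0.78) = 54%. Across the 10-sample scenarios its inflation ran from 2 to 227 times.
- Cox-Reid with a t reference: about nominal. The intended figure is 0.05.

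**5. Benjamini-Hochberg at 5%.** With all genes null, the list extends to the p value at which the rejected fraction is 1/0.05 = 20 times that p value. ML Wald rejects 1.9% at p < 0.001, a ratio of 19, so the cut-off lies near 0.001 and the list holds about 20,000 × 0.019 = 380 genes. Simulation at 5/5 and 8/2 gave roughly 300–480 (ML Wald), 0–6 (likelihood ratio), 8–150 (shrunken Wald) and 0–2 (moderated t-test).

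**The case against.** The strongest reply is that the plan names no Wald or likelihood-ratio test. A negative binomial comparison also covers exact, moderated and t- or F-referenced versions. This stands. A reader might infer that the plan's test has a 9–12% error rate, that 5% is not achieved for any gene, or that hundreds of false genes should be expected. The documents support none of these. Each belongs to a particular implementation, and the hundreds belong to the worst one.

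It does not remove the point. The wording permits the poorly calibrated versions, and shrinkage alone with a normal reference still misses 5% and leaves an inflated tail.

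The synopsis sentence concerns diseased versus normal skin, which could reach 10 v 10 libraries. The 9–12% range does not apply there; about 6–8% does. The responder comparison in section 3.1 has 10 patients at most.

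Multiplicity is the larger defect. At 5% in a single test, a perfectly calibrated method would call 20,000 × 0.05 = 1,000 null genes. The plan has no correction, so the false-discovery figures show what a correction alone would leave unsolved.

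Finally, this is a pilot and a later SAP is promised. That lowers the urgency. But the SAP is to record modifications to the analysis already described, so the present wording is the default, and the study is unblinded.

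**Conclusion.** The point holds in conditional form. On 10 samples, null rejection at nominal 5% is about 12% (gene-wise ML Wald), 9% (likelihood ratio) or 6–8% (shrunken-dispersion Wald with a normal reference). At 10 v 10 these become about 8%, 7% and 6%. Tail inflation means that false-discovery control alone would not make the gene list reliable unless the test is also calibrated.

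The size figures at 5% changed little over the means, dispersions and splits tried. The false-gene counts depend more on the assumed 20,000 genes and on how dispersion varies between genes. All of them assume patient-level values; analysing single cells as independent units would be a different problem. The quasi-likelihood F-test recommended below was not itself simulated. The support for a small-sample reference comes from the Cox-Reid t version, the log-count t-test and the moderated t-test. The change should be made, but it does not by itself invalidate the study.

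**What to change.** In the synopsis and section 13.3, specify a small-sample-calibrated test on one value per patient and cell population (and per skin type where diseased and normal skin are compared). Two options are suitable:
- a negative binomial quasi-likelihood F-test with empirical-Bayes dispersions, which stays within the plan's negative binomial wording;
- a moderated t-test on log counts.

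State that it is applied with false-discovery control. Report the number of genes called against its distribution under permuted group labels. Treat this as a descriptive check, because it is coarse for uneven splits: 8/2 has only 45 relabellings, so the smallest permutation p value is 1/45 = 0.022, and at 9/1 it is 1/10 = 0.10.

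The cost is SAP wording and standard free software. The downside is that fewer genes will be called significant.
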